5.1.3.2 Concomitant medication start date

Concomitant treatments with partial start dates will have the date or dates imputed. Partial concomitant treatment start dates are imputed with reference to the first administration of study treatment within this study in accordance with the rules outlined below.

	Day	Month	Year	
Partial Concomitant medication (CMD) Start Date	Not used	MON	YYYY	
Treatment Start Date	Not used	TRTM	TRTY	

The following matrix explains the logic behind the imputation.

Comparison of month section	MON missing	MON <trtm< th="">MON=TRTM	MON>TRTM	</trtm<>	MON=TRTM	MON>TRTM
YYYY missing	(C)	(C)	(C)	(C)
	Uncertain	Uncertain	Uncertain	Uncertain
YYYY <trtm< td="">(D) =	(A) =	(A) =	(A) =	</trtm<>	(D) =	(A) =	(A) =	(A) =
	01JULYYYY	15MONYYYY	15MONYYYY	15MONYYYY
	Before Treatment Start	Before Treatment Start	Before Treatment Start	Before Treatment Start
YYYY=TRTY	(C) Uncertain	(A) = 15MONYYYY Before Treatment Start	(C) Uncertain	(B) = 01MONYYYY After Treatment Start
YYYY>TRTY	(E) = 01JANYYYY After Treatment Start	(B) = 01MONYYYY After Treatment Start	(B) = 01MONYYYY After Treatment Start	(B) = 01MONYYYY After Treatment Start

The following table is the legend to the logic matrix.

Relationship	
Before Treatment start	Partial date indicates CMD start date prior to Treatment Start Date in this study
After Treatment start	Partial date indicates CMD start date after Treatment Start Date in this study
Uncertain	Partial date insufficient to determine relationship of CMD start date to Treatment Start Date in this study
Imputation calculation	

Relationship	
NC/Blank Uncertain	No convention
(A) Before Treatment Start	15MONYYYY
(B) After Treatment Start	MAX(01MONYYYY, Treatment Start Date +1)
(C) Uncertain	IF CMDTYP IN (1, 3) THEN Treatment Start Date -1 ELSE IF CMDTYP IN (. 2) THEN Treatment Start Date +1
(D) Before Treatment Start	01JULYYYY
(E) After Treatment Start	01JANYYYY

To compute concomitant start date:

- 1. If the concomitant start date year value is missing, the imputed concomitant start date is set to one day prior to study treatment start date.
- 2. If the concomitant start date year value is less than the study treatment start date year value, the concomitant medication started before study treatment. Therefore:
 - a. If the concomitant month is missing, the imputed concomitant start date is set to the mid-year point (01JULYYYY).
 - b. Else if the concomitant month is not missing, the imputed concomitant start date is set to the mid-month point (15MONYYYY).
- 3. If the concomitant start date year value is greater than the study treatment start date year value, the concomitant started after study treatment. Therefore:
 - a. If the concomitant month is missing, the imputed concomitant start date is set to the year start point (01JANYYYY).
 - b. Else if the concomitant month is not missing, the imputed concomitant start date is set to the month start point (01MONYYYY).
- 4. If the concomitant start date year value is equal to the study treatment start date year value:
 - a. And the concomitant month is missing or the concomitant month is equal to the study treatment start date month, then the imputed concomitant start date is set to one day prior to study treatment start date.
 - b. Else if the concomitant month is less than the study treatment start date month, the imputed concomitant start date is set to the mid-month point (15MONYYYY).
 - c. Else if the concomitant month is greater than the study treatment start date month, the imputed concomitant concomitant start date is set to the month start point (01MONYYYY).

If complete (imputed) concomitant end date is available and the imputed concomitant start date is greater than the (imputed) concomitant end date, then imputed concomitant start date should be set to the (imputed) concomitant end date.

5.1.4 Other imputations

5.1.4.1 Medical history date of diagnosis imputation

Completely missing dates and partially missing end dates will not be imputed. Partial dates of diagnosis will be compared to the treatment start date.

- If diagnosis year < study treatment start date year and diagnosis month is missing, the imputed diagnosis date is set to the mid-year point (01JULYYYY)
- Else if diagnosis month is not missing, the imputed diagnosis date is set to the mid-month point (15MONYYYY)
- If diagnosis year = study treatment start date year and (diagnosis month is missing OR diagnosis month is equal to study treatment start month), the imputed diagnosis date is set to one day before study treatment start date

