#### **4.1 Inclusion criteria**

Patients eligible for inclusion in this study must meet all of the following criteria:

1. Signed informed consent must be obtained prior to participation in the study.
2. Patient must be able to understand and communicate with the investigator and comply with the requirements of the study.
3. Male or non-pregnant, non-lactating female patients at least 50 years of age.
4. Diagnosis of GCA classified according to the following criteria:
  - Age at onset of disease  $\geq$  50 years.
  - History of ESR  $\geq$  30 mm/hr or CRP  $\geq$  10 mg/L.
  - Unequivocal cranial symptoms of GCA (new-onset localized headache, scalp or temporal artery tenderness, ischemia-related vision loss, or otherwise unexplained mouth or jaw pain upon mastication) **AND/OR** symptoms of polymyalgia rheumatica (PMR defined as shoulder and/or hip girdle pain associated with inflammatory morning stiffness).
  - Temporal artery biopsy revealing features of GCA **AND/OR** evidence of large-vessel vasculitis by angiography or cross-sectional imaging study such as magnetic resonance angiography (MRA), computed tomography angiography (CTA), positron emission tomography-computed tomography (PET-CT), or ultrasound.
5. Patients with new onset GCA or relapsing GCA:
  - Definition new onset: diagnosis of GCA within 6 weeks of Baseline Visit.
  - Definition relapsing GCA: diagnosis of GCA (in accordance with inclusion criterion no. 4)  $>$  6 weeks before Baseline Visit and in the meantime achieved remission (absence of signs and symptoms attributable to GCA and normalization of ESR ( $<$  30 mm/hr) and CRP ( $<$  10.0 mg/L) included) including previous treatment with  $\geq$  25 mg/day prednisolone equivalent for  $\geq$  2 weeks.
6. Active disease as defined by the presence of signs and symptoms of GCA (cranial or PMR) and elevated ESR  $\geq$  30 mm/hr, or CRP  $\geq$  10 mg/L, attributed to active GCA within 6 weeks of Baseline.
7. Prednisolone dose of 25-60 mg/day at Baseline.
8. Patients taking MTX ( $\leq$  25 mg/week) are allowed to continue their medication provided they have taken it for at least 3 months and are on a stable dose for at least 4 weeks prior to randomization and if they are on a stable folic acid treatment before randomization.

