## 6.1 Screening

Screening will be flexible (up to 6 weeks in duration) to be able to adhere to the protocol-defined prednisolone taper regimen (maximum dose of 60 mg at Baseline) and to allow sufficient time for the washout of relevant medications. During Screening, the patient will be evaluated for eligibility in addition to all other assessments indicated in Table 6-1.

Screening will consist of 2 consecutive visits. During Screening Visit 1, initial assessments will be performed as outlined in Table 6-1. At that visit, it will be determined whether a washout period is required. Screening Visit 2 will be performed as follows:

- If the washout period is  $\leq$  4 weeks the investigator should proceed directly to Screening Visit 2 on the same day and complete all assessments in the next 4 weeks prior to randomization.
- If the washout period is more than 4 weeks, the patient will be instructed to initiate the necessary washout regimen and return for Screening Visit 2 at 4 weeks prior to randomization.

The rationale is that in all cases Screening Visit 2 must occur within the 4 weeks prior to randomization and should ideally be performed no less than 2 weeks prior to randomization to allocate time for laboratory analyses and shipment of medication.

All patients evaluated at Screening Visit 1 and 2 for eligibility should not be screen failed on the basis of a medication requiring washout, unless the patient will be unable to complete the washout in the appropriate time frame before randomization.

Screening Visit 1 and Visit 2 may be performed on the same day if possible.

It is permissible to re-screen a patient once if s/he fails the initial Screening; however, each case must be discussed and agreed with the Sponsor on a case-by-case basis.

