#### **9.4.5 Subgroup analyses**

Subgroup analyses of the primary endpoint will be performed:

- To investigate the difference between new-onset (diagnosed within 6 weeks of baseline) and refractory patients (diagnosed  $\geq$  6 weeks before baseline and previous treatment with  $\geq 25$  mg/day prednisolone for  $\geq 2$  consecutive weeks) given the homogenous nature of the disease.
- To allow assessment of the benefit/risk of secukinumab in patients who need a higher ( $> 40$  mg/day) versus lower ( $\leq 40$  mg/day) initial dose of prednisone will also be provided.

The posterior distributions for the estimate of the RD, OR, and RR will be derived and the associated median and 95% credibility interval will be presented.

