2.1.1.6 Baseline date

Baseline date is referred to as Day 1 of the study. It is defined as the date of first administration of study treatment in this study for treated patients. If a patient is randomized but not treated then the baseline date is defined as the date of randomization.

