2.2.1 Subgroup of interest

The subgroups of interest for this study are:

- GCA diagnosis
 - New onset GCA (defined as GCA diagnosis date within 6 weeks of Baseline visit date or there is a protocol deviation, in relation to inclusion criteria 5, regardless of protocol deviation discrepancy status)
 - Relapsing disease GCA (defined as GCA diagnosis date > 6 weeks from Baseline visit
- Baseline co-administered prednisolone treatment
 - $\geq 40 \text{ mg/day}$
 - < 40 mg/day

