2.3.2 Demographics and other baseline characteristics

Demographics and other baseline characteristics data will be summarized for each treatment group and overall (i.e. all patients) for the FAS. Patients will be analyzed according to the treatment assigned at the last randomization (see Section 2.2 for further details).

Descriptive statistics will be presented for the following continuous demographic and other baseline characteristics variables:

- Age (years)
- Height (cm)
 - Note: This will be presented for each treatment group and overall and in addition for each sex category in each treatment group and overall.
- Weight (kg)
 - Note: This will be presented for each treatment group and overall and in addition for each sex category in each treatment group and overall.
- Body mass index (BMI) (kg/m²)
 - Defined as: (body weight in kg) / (height in meters)²

For BMI, height and body weight used is the last value prior to first administration of study treatment. If there is no weight recorded prior to taking the study treatment, BMI will be missing.

Note: This will be presented for each treatment group and overall and in addition for each sex category in each treatment group and overall.

- Time since diagnosis of GCA (years)
 - Defined as: (date of Visit 1 date of diagnosis of GCA) / 365.25 For handling of missing or incomplete GCA diagnosis dates, refer to Section 5.1.4.
- Time since first GCA symptom (years)
 - Defined as: (date of Visit 1 date of first GCA symptom) / 365.25
 For handling of missing or incomplete first GCA symptom dates, refer to Section 5.1.4.
- GCA diagnosis (New onset GCA, Relapsing disease GCA)
- Baseline co-administered prednisolone treatment (≥ 40 , < 40 mg/day)

The number and percentage of patients in each category of the following categorical variables overall will be presented:

- Weight group $(< 70, \ge 70 \text{ to } < 90, \ge 90 \text{ kg})$
- Current smoking status (Current, Former, Never)
- Race (White, Black or African American, Asian)
- Sex (Male, Female)

All important demographics and other baseline characteristics data will be listed by treatment group, center, and subject number for the RAS.

In addition, for the legal requirements of clinicaltrials.gov and EudraCT, the following age categories will also be presented:

- 18 to < 65 years

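### A GCA diagnosis known only as the treatment-start year is imputed to the day before first dose, so time since diagnosis to Visit 1 comes out negative and contradicts relapsing eligibility

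*SAP*

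**What the plan says.** SAP 2.3.2 lists time since GCA diagnosis as a baseline characteristic: Visit 1 date minus diagnosis date, divided by 365.25. It adds: "For handling of missing or incomplete GCA diagnosis dates, refer to Section 5.1.4". The rule found there, SAP 5.1.4.1, has three parts:

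- diagnosis year before the treatment-start year, month missing: 1 July of that year;
- month known: the 15th of that month;
- diagnosis year equal to the treatment-start year, with the month missing or equal to the start month: "the imputed diagnosis date is set to one day before study treatment start date".

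No part limits the imputed date to Visit 1 or earlier.

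On timing, SAP 2.1.1.6 says of the Baseline date: "It is defined as the date of first administration of study treatment in this study for treated patients". Protocol 6.1 says that Screening Visit 2 "should ideally be performed no less than 2 weeks prior to randomization", and Visit 1 is on the same day or earlier. Protocol 3.1 allows at most 6 weeks of screening.

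On classification, Protocol 4.1 has "Definition new onset: diagnosis of GCA within 6 weeks of Baseline Visit". Relapsing disease requires diagnosis more than 6 weeks before Baseline, with further conditions. Protocol 9.4.5 plans a subgroup analysis "To investigate the difference between new-onset (diagnosed within 6 weeks of baseline) and refractory patients". SAP 2.2.1 keeps the 6-week split but extends new onset with the words "or there is a protocol deviation, in relation to inclusion criteria 5, regardless of protocol deviation discrepancy status".

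**The concern.** The imputation is anchored to first dose, while the duration it feeds is anchored to Visit 1, which comes earlier. The rule can therefore place diagnosis after the visit from which its age is counted, and the baseline table would then contain impossible negative durations.

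The same imputed date lies one day before Baseline whatever the patient's history. For someone enrolled as relapsing it contradicts the criterion under which they entered. If it also sets the subgroup, it moves that patient into the wrong stratum of the first planned subgroup analysis of the primary endpoint. It would also affect the requirement in SAP 2.5.4 of at least 5 patients per subgroup.

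**Working it through.** The documents give no figure to reproduce here, so the check applies the stated rules.

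**Negative duration (same year, month missing).** Let T be the first-dose date.

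- Imputed diagnosis date = T - 1 (SAP 5.1.4.1).
- Visit 1 = T - k, with k from 0 to 42 days (Protocol 3.1).
- Time since diagnosis = (T - k) - (T - 1) = 1 - k days (SAP 2.3.2).

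| k (days) | 1 - k (days) | years (/365.25) |
|---|---|---|
| 1 | 0 | 0 |
| 2 | -1 | -0.003 |
| 14 | -13 | -0.036 |
| 28 | -27 | -0.074 |
| 42 | -41 | -0.112 |

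The value is negative for 41 of the 43 possible gaps. Gaps of 0 or 1 day are unrealistic, because the central-laboratory tuberculosis result from Screening Visit 2 must be known before randomization (Protocol 6.1.5). Counted to the Baseline date instead, the value is T - (T - 1) = +1 day for every k.

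**Relapsing patients.** The imputed date is 1 day before Baseline; eligibility requires more than 42 days. Under an assumed first dose on 30 September 2020, a relapsing patient with only the year recorded must have been diagnosed between 1 January and 18 August, that is 273 to 43 days earlier. For an assumed first dose on 1 March 2020 the range is 60 to 43 days. Before mid-February no eligible relapsing patient can have a diagnosis in the same year.

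**Month equal to the start month.** Here the 15th-of-month rule also matches, and the SAP does not say which governs. With first dose on 30 September and Visit 1 on 16 September (k = 14), the day-before rule gives 16 - 29 = -13 days and the 15th rule gives 16 - 15 = +1 day. With first dose on 15 September and Visit 1 on 18 August 2020, they give -27 and -28 days. In this second case the recorded month itself places diagnosis after Visit 1, so the negative sign is not created by the rule.

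**Other branches.** With first dose on 15 September and Visit 1 on 18 August 2020, a diagnosis in 2019 with month missing gives +1.13 years, and March 2020 gives +0.43 years.

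**Subgroup effect, if imputed dates are used.** Subgroup counts are assumed; priors are those of the primary analysis.

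- 6/12 on secukinumab v 2/12 on placebo: posterior median risk difference 0.316 (95% credible interval 0.041 to 0.588). One secukinumab patient wrongly added to new onset gives 0.279 (6/13) or 0.353 (7/13). One lost from a relapsing group of the same size gives 0.359 (6/11) or 0.272 (5/11). The shift is about 0.04 against a width of 0.588 - 0.041 = 0.547.
- 3/6 v 1/6 in a small relapsing group: 0.313 (-0.035 to 0.661), moving to 0.406 (3/5) or 0.221 (2/5). The shift is about 0.09 against a width of 0.661 + 0.035 = 0.696.

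**The case against.** The best defence is that the case is narrow and rare. Only one branch is affected: earlier-year dates go to 1 July and known months generally to the 15th. Criterion 5 requires diagnosis to be placed relative to 6 weeks before Baseline, which a bare year usually cannot show. Protocol 8.1 requires full verification of eligibility, and Protocol 8.3 has missing values queried. All of this stands and limits the number of patients. It does not repair the rule, which the SAP includes for exactly this type of date.

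Four stronger readings are tempting, and the documents do not support them:

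- That every partial diagnosis date yields a negative duration. The other branches above show otherwise.
- That imputed dates do misclassify patients. SAP 2.2.1 does not cite 5.1.4 and is silent on whether imputed dates count, so this harm is conditional.
- That the day-before rule also corrupts first-symptom durations. SAP 2.3.2 does say "For handling of missing or incomplete first GCA symptom dates, refer to Section 5.1.4", but the visible text of 5.1.4 covers only diagnosis dates, and nothing says that the rule is reused.
- That the criterion-5 clause in SAP 2.2.1 is an error or makes the subgroups overlap. It is prespecified, and SAP 1 says that the SAP includes deviations from the protocol. It also places patients whom Protocol 9.4.5 leaves in neither group, such as those diagnosed more than 6 weeks earlier without the required prednisolone treatment. The relapsing definition is cut off in the available text, and the coding of these deviations is in edit check specifications that were not supplied. What remains is that SAP Section 4 declares the prednisolone dose cut as a subgroup change but not this one.

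**Conclusion.** The concern holds for a diagnosis dated only to the treatment-start year. There the rules as written return 1 - k days, which is -13 to -41 days for gaps of 14 to 42 days, and the imputed date cannot be right for a relapsing patient. When the recorded month is the start month, the SAP is ambiguous rather than clearly wrong.

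The consequence is minor: implausible entries in one baseline row and, only if imputed dates set the subgroup, possible misplacement of a few patients in one subgroup table. The risk-difference shifts of about 0.04 to 0.09 rest on assumed counts and are small against the interval widths. The documents do not say how many patients have such dates. A reader might infer that the main result is at risk. It is not: neither the primary analysis nor the go criteria use the diagnosis date. The criterion-5 clause is a disclosure point only.

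**What to change.** - In SAP 2.3.2, count time since diagnosis to the Baseline date as defined in SAP 2.1.1.6. Leave the duration missing for month-missing dates in patients enrolled as relapsing: counting to Baseline corrects the sign, but +1 day would still be false for them.
- In SAP 5.1.4.1, state which rule governs when the recorded month equals the start month.
- In SAP 2.2.1, state that imputed dates do not set the new-onset/relapsing subgroup. Take it from the eligibility data on which limb of criterion 5 was met, and otherwise show the patient as unknown.
- In SAP Section 4, list the criterion-5-deviation clause as a change from Protocol 9.4.5.

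The cost is a few sentences and a small derivation change. Every duration lengthens by the patient's screening gap, at most 42 days (42/365.25 = 0.115 years), and a few patients may appear as missing or unknown. If the eCRF does not record which limb was met, more month-missing patients will be unknown.

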5.2 Adverse events coding/grading

Reporting of AEs will be based on MedDRA version 23.0 or higher. For the analysis purpose, the latest version of MedDRA available at CDBL will be used for reporting activity.

5.3 Laboratory parameters derivations

All laboratory parameters were analyzed at a central laboratory with the exception of the following which were analyzed locally:

- ESR
- Urinalysis
- Urine pregnancy test

If the statistics and statistical programming team receive any laboratory data in conventional rather than SI units, these will be converted to SI units using the global conversion library in GPS.

5.3.1 Imputation rules

If laboratory values are provided as "<X" (i.e. below limit of detection) or ">X", prior to conversion of laboratory values to SI unit, these numeric values are set to X.

The following rules will be applied to derive the WBC differential counts when only percentages are available for a xxx differential:

• xxx count = (WBC count) * (xxx %value / 100)

5.4 Questionnaires

5.4.1 EQ-5D

This questionnaire is used to assess the health status in adults. The measure is divided into 2 distinct sections.

The first section includes one item addressing each of 5 dimensions:

- mobility
- self-care
- usual activity
- pain/discomfort
- anxiety/depression

Patients rate each of these items from "no problems", "slight problems", "moderate problems", "severe problems", or "extreme problems". A composite health index is then defined by combining the levels for each dimension.

The second section measures self-rated (global) health status utilizing a vertically oriented VAS where 100 represents the "best possible health state" and 0 represents the "worst possible health state." Respondents are asked to rate their current health by placing a mark along this continuum. The recall period is "today".

Computing EQ-5D-5L utility index values

The following derivation is based on the SPSS value set - Germany - EQ-5D-5L using the German (GER) Ludwig value set version 1.1 (last updated 17FEB2020).

```
******************
*SPSS syntax code for the computation of index*
*values with the GER TTO value set*
**********************
IF (mobility=1) disut mo=0.
IF (mobility=2) disut mo=0.026.
IF (mobility=3) disut mo=0.042.
IF (mobility=4) disut mo=0.139.
IF (mobility=5) disut mo=0.224.
IF (selfcare=1) disut sc=0.
IF (selfcare=2) disut sc=0.050.
IF (selfcare=3) disut sc=0.056.
IF (selfcare=4) disut sc=0.169.
IF (selfcare=5) disut_sc=0.260.
IF (activity=1) disut sc=0.
IF (activity=2) disut sc=0.036.
IF (activity=3) disut sc=0.049.
IF (activity=4) disut sc=0.129.
IF (activity=5) disut sc=0.209.
IF (pain=1) disut sc=0.
IF (pain=2) disut_sc=0.057.
IF (pain=3) disut_sc=0.109.
IF (pain=4) disut_sc=0.404.
IF (pain=5) disut sc=0.612.
IF (anxiety=1) disut sc=0.
IF (anxiety=2) disut sc=0.030.
IF (anxiety=3) disut sc=0.082.
IF (anxiety=4) disut sc=0.244.
IF (anxiety=5) disut sc=0.356.
Compute disut total= disut mo +disut sc +disut ua +disut pd +disut ad.
Compute EQindex = 1-disut total.
execute.
```

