#### 6.5.2.1.4 EuroQol 5D

The EQ-5D-5L is a widely used, self-administered questionnaire designed to assess health status in adults ([Xu et al 2011](#), [Mc Clure et al 2017](#)). The purpose of the EQ-5D-5L in this study is to assess the general health status of the patients. The measure is divided into 2 distinct sections. The first section includes 1 item addressing each of 5 dimensions (mobility, self-care, usual activity, pain/discomfort, and anxiety/depression). Patients rate each of these items from “no problem”, “slight problems”, “moderate problems”, “severe problems”, “extreme problems/unable.” A composite health index is then defined by combining the levels for each dimension. The second section of the questionnaire measures self-rated (global) health status utilizing a vertically oriented VAS where 100 represents the “best possible health state” and 0 represents the “worst possible health state.” Respondents are asked to rate their current health by placing a mark along this continuum. The recall period is “today,” and the questionnaire requires approximately 5 to 10 minutes to complete.

The EQ-5D-5L contains 6 items designed to assess health status in terms of a single index value or health utility score. One of the strengths of the EQ-5D-5L approach is that it allows “weighting” by the patient of particular health states and the generation of patient utilities. Published weights are available that allow for the creation of a single summary health utility score. Overall scores range from 0 to 1, with lower scores representing a higher level of dysfunction. The EQ5D is filled in by the patient at the visits specified in [Table 6-1](#) prior to study drug administration.

A series of 12 horizontal black bars of varying lengths, decreasing from left to right. The first bar is the longest, followed by a short black bar, then a long black bar, and so on, ending with the shortest black bar on the right. The bars are set against a white background.

[REDACTED]

[REDACTED]

[REDACTED]

[REDACTED]

[REDACTED]

[REDACTED]

[REDACTED]

[REDACTED]

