2.1 Data analysis general information

This study will be conducted under the sponsorship of Novartis. The analysis will be performed by Novartis NBS CONEXTS or a designated contract research organization (CRO) (if applicable).

All analyses will be performed using SAS® statistical software (Version 9.4 or a more recent version), unless otherwise noted.

The independent statistical and statistical programming team will perform the unblinded statistical analyses. These analyses are detailed in the respective data monitoring committee (DMC) and IA SAPs.

Data will be summarized with respect to demographic and other baseline characteristics along with safety observations.

Descriptive statistics (the number of non-missing observations [n], mean, median, standard deviation [SD], minimum, and maximum values) will be presented for continuous variables.

For categorical variables, the number and percentage of each category within a variable will be calculated for non-missing data. If a count of zero is obtained for categorical data, only the zero count will be displayed. If no treatment group satisfies a category, then the category will be

displayed, unless stated otherwise. A row (category) denoted 'Missing' will be included in count tabulations if a non-zero count of missing values is present. In addition, the corresponding percentage for this row will be displayed.

All data will be listed by center and subject number, unless otherwise stated.

It is planned that the data from all centers that participate in this study will be used so that an adequate number of patients will be available for analysis.

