The EQ-5D is a questionnaire with 5 questions (regarding mobility, self-care, usual activities, pain/discomfort, and anxiety/depression) each with 5 categories and a health state assessment from 0 (worst possible health state) to 100 (best possible health state). The number and percentage of patients in each of the 5 categories for each question will be presented by study visit and treatment group. Descriptive summary statistics will be provided for the change from baseline of health state assessment (known as EQ-5D-5L VAS) and EQ-5D-5L utility index (see Section 5.4.1 for further details) by study visit and treatment group.

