STRATA <stratavar>;

RUN;
```

The option OUTSIDE(0.15) reserves 15% of the vertical graph window for the at-risk table. It can be adjusted.

SAS Codes for Kaplan-Meier Table

The summary statistics for time to event analysis will be performed using SAS procedure PROC LIFETEST.

Note that for this illustrative example:

- the data are stored in the file data set
- timevar = survival time
- censorvar = censoring variable (Note: 1 indicates a censored time)
- stratavar = stratification variable

SAS code for logistic regression

For the appropriate treatment difference, the treatment cohorts should be sorted or coded appropriately before using this model.

The analysis will be performed using SAS procedure PROC GENMOD as below. Note that for this illustrative example:

- the data are stored in the file data set
- treatmentvar = treatment cohort variable
- responsevar = dependent variable
- catvar = categorical variable of interest

• contvar = continuous variable of interest

```
PROC GENMOD DATA = <data_set>;
CLASS <treatmentvar> <catvar>
TABLES <responsevar> = <treatmentvar> <catvar> <contvar> / DIST=BINOMIAL
LINK=LOGIT;
LSMEANS <treatmentvar> / PDIFF CL;
RUN;
```

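### SAP 5.4.1: the EQ-5D-5L utility code stores four of the five dimensions in one variable and sums three variables it never creates, so as written it yields no utility index

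*SAP*

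**What the plan says.** SAP Section 2.10 commits to descriptive statistics for change from baseline in the "EQ-5D-5L utility index (see Section 5.4.1 for further details) by study visit and treatment group". Section 5.4.1 supplies SPSS syntax based on a named and dated German value set, with five decrements for each of the five dimensions.

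- Mobility is assigned to its own variable, for example "IF (mobility=5) disut mo=0.224".
- Self-care is assigned to `disut_sc`, which is correct.
- Usual activity, pain and anxiety are also assigned to `disut_sc`, for example "IF (pain=4) disut_sc=0.404" and "IF (anxiety=5) disut sc=0.356".
- The total is "Compute disut total= disut mo +disut sc +disut ua +disut pd +disut ad", and the index is 1 minus that total.

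On software, SAP Section 2.1 states: "All analyses will be performed using SAS® statistical software (Version 9.4 or a more recent version), unless otherwise noted". On the scale of the score, Protocol Section 6.5.2.1.4 states: "Overall scores range from 0 to 1, with lower scores representing a higher level of dysfunction".

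**The concern.** The total needs five variables and the code creates two, so the derivation does not produce the quantity that Section 2.10 promises. No other section repairs it, and SAP Section 4 (changes to protocol-specified analyses) does not mention it.

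The block must be translated from SPSS to SAS, and each programmer would have to repair it without written guidance. A failed run or an all-missing column would be noticed. A repair that skips missing terms, such as the SAS SUM function, would not announce itself: it returns plausible numbers that leave out self-care, activity and pain, and pain carries the largest decrement. Comparing the output with the protocol's 0 to 1 range would not expose this, because the wrong index lies inside that range and the intended one does not.

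**Working it through.** **Is it a PDF artefact?** Lost underscores are, and they are ignored here. The suffix is not: `sc` stands on all 15 activity, pain and anxiety lines, some with the underscore intact, while the total line in the same block keeps `ua`, `pd` and `ad`.

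**Inputs** (decrements as printed in SAP 5.4.1, levels 1 to 5):

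| Dimension | Decrements | Assigned to | Total expects |
|---|---|---|---|
| Mobility (MO) | 0, 0.026, 0.042, 0.139, 0.224 | `disut_mo` | `disut_mo` |
| Self-care (SC) | 0, 0.050, 0.056, 0.169, 0.260 | `disut_sc` | `disut_sc` |
| Activity (UA) | 0, 0.036, 0.049, 0.129, 0.209 | `disut_sc` | `disut_ua` |
| Pain (PD) | 0, 0.057, 0.109, 0.404, 0.612 | `disut_sc` | `disut_pd` |
| Anxiety (AD) | 0, 0.030, 0.082, 0.244, 0.356 | `disut_sc` | `disut_ad` |

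The plan states no utility value to reproduce, so the code was traced over all 5^5 = 3125 health states. States are written in the order MO, SC, UA, PD, AD.

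**(a) As written.** `disut_ua`, `disut_pd` and `disut_ad` are undefined in 3125 of 3125 states. SPSS rejects the COMPUTE; a SAS translation with `+` returns missing throughout.

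**(b) Intended index under the printed decrements:** 1 − (MO + SC + UA + PD + AD).

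- Maximum total decrement: 0.224 + 0.260 + 0.209 + 0.612 + 0.356 = 1.661.
- Range: 1 − 1.661 = −0.661 up to 1.000.
- States below 0: 471 of 3125.

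**(c) Conditional index, if undefined terms are skipped or set to zero.** With complete responses the anxiety block is the last to write to `disut_sc`, so the result is 1 − (MO + AD).

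- Range: 1 − (0.224 + 0.356) = 0.420 up to 1.000.
- It equals (b) only when SC, UA and PD are all at level 1: 5 × 5 = 25 states. It is too high in the other 3125 − 25 = 3100.
- Largest gap: 0.260 + 0.209 + 0.612 = 1.081, which is 1.081/1.661 = 65% of the maximum decrement.

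| State or change | Intended (b) | Conditional (c) |
|---|---|---|
| 11141 | 1 − 0.404 = 0.596 | 1.000 |
| 33333 | 1 − 0.338 = 0.662 | 1 − 0.124 = 0.876 |
| 55555 | −0.661 | 0.420 |
| 22242 to 22222 | 0.801 − 0.454 = +0.347 | 0.944 − 0.944 = 0.000 |
| 33343 to 22222 | 0.801 − 0.367 = +0.434 | 0.944 − 0.876 = +0.068 |

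**The case against.** The strongest reply is that this is a loud and recoverable transcription slip. The code fails at the first run, the item labels and the total line show what was meant, and the SAP names the value set and its version, so a competent programmer would put it right. This stands in part: the intended mapping is recoverable, and the figures under (c) depend on a repair that no section describes. But the written derivation still does not work, and how to repair it should not be left to individual judgement.

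The stakes are also low. The EQ-5D analysis in Protocol Section 9.5.1 names only category counts and the health-state score; the utility index summary is added by SAP 2.10, is descriptive, and feeds no test or decision rule. That is accepted and limits the weight of the point.

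Three further qualifications are fair. The decrements are taken as printed and were not checked against the value set. A test on 55555 alone uses only level-5 values and would miss a misprint at levels 2 to 4. And the protocol's 0 to 1 sentence is a general description of the instrument, not a prescribed check; changing it needs a formal amendment.

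**Conclusion.** The concern holds. Followed literally, SAP 5.4.1 gives no utility index for any patient, and nothing else in the documents corrects it. This rests on reading the code alone.

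The larger figures (3100 of 3125 states too high, by up to 1.081; a true gain of +0.347 shown as zero) apply only if the undefined terms are skipped or set to zero, and they assume complete responses and the decrements as printed. The effect is confined to the utility index part of the EQ-5D secondary endpoint. The EQ VAS, the category counts, the primary endpoint and the GO criteria are unaffected. The correction should be made, but nothing central to the trial turns on it.

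**What to change.** In SAP 5.4.1, change the assignment target on 15 lines: activity to `disut_ua`, pain to `disut_pd`, anxiety to `disut_ad`. Then check the program in two ways:

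- **Mapping.** Under the printed decrements, 55555 must give −0.661. One state per dimension shows whether each reaches the total: 51111 = 0.776, 15111 = 0.740, 11511 = 0.791, 11151 = 0.388 and 11115 = 0.644 (each 1 minus its level-5 decrement).
- **Values.** Compare all 25 decrements with the value set that the SAP names.

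The SAP change costs almost nothing and touches no other analysis. The 0 to 1 range in Protocol 6.5.2.1.4 should also be corrected, since 471 of 3125 states fall below 0 with the SAP's own decrements. Because protocol text changes only by approved amendment, that sentence can wait for the next one.

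A minor note for the same SAP revision: the illustrative logistic template in Section 5.5 has "TABLES <responsevar> = <treatmentvar> <catvar> <contvar> / DIST=BINOMIAL" where PROC GENMOD needs a MODEL statement. It also lacks ALPHA=0.2 and EXP, which are needed for the odds ratio with 80% interval that Section 2.5.4 correctly specifies. This is a template slip, not an error of method.
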